3.1.3 Post Transplant Maintenance Therapy

One approach to improving disease control after HDM/ASCT is the use of post-transplant interventions, such as interferon and, more recently, anti-angiogenic agents such as thalidomide and lenalidomide. The use of thalidomide as post-transplant maintenance has been studied in several randomized trials^{24,25,27}. The IFM 99-02 trial randomized patients after tandem autologous transplantation (using melphalan 140mg/m² for the first and melphalan 200mg/m² for

MEMORIAL SLOAN-KETTERING CANCER CENTER IRB PROTOCOL

IRB#: 11-107A(12)

the second transplant) to either no maintenance, maintenance with pamidronate or maintenance with thalidomide and pamidronate. Patients received thalidomide for a median of 15 months. The major treatment-related side effect was neuropathy (68% of patients). Patients who received thalidomide had improved EFS and OS. Of note, patients who achieved a VGPR after transplantation did not benefit from thalidomide maintenance²⁷. This suggests that the benefit of post-transplant thalidomide might result from upgrading responses.

New immunomodulatory drugs (IMiDs®) such as lenalidomide are now commonly used in clinical practice. The side effect profile of lenalidomide is superior to that of thalidomide. In normal volunteers the most common adverse events with lenalidomide are rash and pruritus. Phase II trials of lenalidomide plus dexamethasone for upfront therapy of myeloma demonstrate high response rates¹¹. Lenalidomide, a member of the new immunomodulatory class of drugs has recently demonstrated high-response rates and favorable side effect profile in upfront and salvage trials^{28,29}. A Phase II trial at the Mayo Clinic used lenalidomide and dexamethasone as induction therapy. The overall response rate was 91%. The Phase III MM009 trial of lenalidomide and dexamethasone versus dexamethasone alone for relapsed/refractory MM reported response rates of 61% with combination therapy compared to 22% with dexamethasone alone.²⁹ Hence, based on both a more favorable side effect profile and higher CR rates, lenalidomide appears to be a superior drug for maintenance therapy.

In 2010 two large randomized trials were presented both in the meeting of the American Society of Clinical Oncology in Chicago and the meeting of the American Society of Hematology in Orlando exploring the use of single agent lenalidomide as post transplant maintenance therapies.

McCarthy et al. presented the results of CALGB 100104 whose primary endpoint was to investigate the role of maintenance lenalidomide in prolonging time to progression (TTP) following single autologous SCT.³⁰ Patients with chemosensitive disease after an initial autologous SCT were randomized at day 100-110 post-ASCT to lenalidomide 10 mg/day or placebo until disease progression. A total of 554 patients were registered during the third interim analysis, and 33% of the required number of events (progression or death before progression) had been observed. The median follow-up is 17.5 months. The number of events among 231 pts randomized to lenalidomide was 37 compared to 84 among 229 pts randomized to placebo. The one-sided unadjusted P-value was < 0.0001. The estimated hazard ratio was 0.35 (95% CI=0.24, 0.53) corresponding to a 65% reduction in event risk (progression or death) in the lenalidomide arm. The estimated median TTP was 22.5 months for the placebo arm. The preliminary estimated median TTP was 45.5 months for the study arm. Benefits were seen regardless of whether patients received lenalidomide or thalidomide as induction therapy. Comparing lenalidomide versus placebo, post-randomization, pooled Gr 3-5 AEs, there were significantly more episodes of thrombocytopenia (11% versus 3%, p=0.01), neutropenia (44% vs 8%, p<0.0001) and anemia (5% vs 1%, p=0.0082) with lenalidomide. No significant differences in incidence of febrile neutropenia, infection, fatigue, neuropathy, rash, thromboembolic events were seen. Lenalidomide patients discontinued therapy due to AEs more frequently than placebo (13% vs 2%). Attal et al. presented the results of a similar trial performed by the Intergroup Francophone du Myelome that enrolled 614 patients who had undergone autologous stem cell transplantation for non-progressive myeloma within the previous six months³¹. Patients were randomly assigned to placebo (307 patients) or 10 mg to 15 mg of lenalidomide daily (307 patients) until relapse.

MEMORIAL SLOAN-KETTERING CANCER CENTER IRB PROTOCOL

IRB#: 11-107A(12)

After a median follow-up of 24 months, only 25% of the lenalidomide group experienced progression or death compared with 47% of the placebo group. Maintenance with lenalidomide improved three- year PFS from randomization by 34% in the placebo group compared with 68% in lenalidomide group (HR=0.46). Benefits were seen regardless of response to induction therapy¹⁰.

These 2 studies have consolidated the role of maintenance therapy, in particular lenalidomide, after autologous stem cell transplantation. It is unknown whether use of post-transplant maintenance lenalidomide until disease progression will provide similar EFS and OS to either tandem transplantation or a single transplant followed by consolidation and maintenance. This is currently being actively investigated. However, maintenance therapy with low dose lenalidomide has been widely embraced and most patients will be receiving this treatment following HDM/ASCT.

3.2 Rationale for the study

As mentioned above, all patients with multiple myeloma treated with the currently available treatment modalities and strategies will eventually relapse. Patients on maintenance lenalidomide are no exception to this rule. However, it is currently unknown whether these patients whose disease progress, while on low dose lenalidomide as maintenance therapy, will respond to treatment with higher doses (considered standard doses, but for the purpose of this trial referred to as intensification) of lenalidomide. Currently it is widely perceived among physicians that these patients have a disease that is lenalidomide resistant and there is an actual risk of these patients being denied access to a potentially very effective agent, if given at higher (standard) dose.

3.2.1 Rationale for Lenalidomide Intensification Dose

The maximum tolerated dose (MTD) of lenalidomide as a daily dose is 25 mg with dose-limiting toxicity (DLT) being grade 3/4 myelosuppression. The Phase I trial of single agent lenalidomide demonstrated higher response rates with increasing dosage with 20%, 66%, and 69% of patients having at least a minimal response when receiving 10 mg, 25 mg, and 50 mg respectively³². Based on the pharmacokinetic data of the phase I trial, and the favorable toxicity profile observed, a randomized Phase II study has been reported that examined a higher dose with an interrupted schedule: 15 mg twice daily versus 30 mg daily on a 3 weeks on / 1 week off schedule³³. This study examined 70 patients randomized to the two schedules. Fifty-seven patients were analyzed for toxicity and 46 for response. In this heavily pre-treated group of patients, 24% had a CR or PR or minimal response and only 16% had progressive disease. One patient developed grade 3 neuropathy. The most common grade 1 and 2 toxicities were fatigue, self-limited rash, muscle cramps and diarrhea. Grade 3 or 4 myelosuppression was seen in 26% (n=15) of patients. Eleven of these 15 patients had undergone a prior autologous transplant; most (n=11) were on the 15 mg twice a day dose. The daily dosing schedule was felt to be more favorable based on its toxicity profile and simplicity of administration with best opportunity for compliance. There was no evidence that an interrupted schedule enhanced long-term tolerability or response. Thus, there is data supporting the dose related response to lenalidomide and its optimal efficacy/tolerability ratio with 25 mg given daily for 21 days every 28 days.

3.2.2 Rationale for patient population under study

3.2.2.1 Relapse Patterns Post-Autologous Stem Cell Transplantation

The two largest reports of the natural history of relapse post autograft in myeloma were both reported prior to the advent of lenalidomide and bortezomib. Alegre et al. reported on the outcomes of 280 patients who had relapsed after transplantation and had data available in the Spanish registry³⁴. The clinical patterns of relapse fell into one of four categories:

- a) Insidious relapse characterized by asymptomatic elevations of the blood or urine protein occurred in 18% of patients.
- b) Classic relapse characterized by an increase in monoclonal component along with clinical symptoms occurred in 66% of patients
- c) Plasmacytomas occurred in 14% of patients and was characterized by presentation with multiple extramedullary plasmacytomas.
- d) Plasmacytic leukemia as the initial clinical manifestation of relapse occurred in 2% of patients.

Median overall survival after relapse was 14 months for the whole group with a significant difference in the OS of patients with the insidious form of relapse when compared to those with symptomatic or plasma cell leukemia patterns of relapse (18 months vs 12 months v/s 5 months respectively; $p < 0.001$).

Lenhoff et al. reviewed the outcomes of 397 patients who had relapsed after autologous transplantation between 1994 and 1997³⁵. The patterns of relapse after transplantation were classified based on a modification of a model presented by Alegre *et al.* The insidious pattern accounted for 31% , the classical pattern for 51%, and the plasmacytoma pattern for 14% of all relapses and characterized by bone marrow or extramedullary plasmacytoma with minor or no other signs of relapse and finally transformed disease which accounts for 4% of relapses and presents as plasma cell leukemia or immunoblastic lymphoma. No association was found between the pattern of relapse and any of the clinical features at diagnosis. The insidious form of relapse was significantly less common in patients who had attained complete response after transplantation than in patients who had not (17% versus 40% of the relapses, respectively). Patients who relapsed with transformed disease had a significantly shorter duration of first response after transplantation (median 3 months) compared to patients relapsing with an insidious (median 20 months), classical (median 20 months) or plasmacytoma (median 24 months) pattern. Survival was related to the type of relapse and longest in patients with the insidious pattern (median 39 months) and shortest in patients with transformed disease (median 2 months). Patients with the classical pattern of relapse were subdivided into two groups; those with skeletal clinical symptoms only at relapse (n=46) and those with additional symptoms such as cytopenias, hypercalcemia, renal insufficiency, etc. (n=37). Patients with only skeletal symptoms had a median survival after relapse of 30 months, while those with additional symptoms had a significantly shorter median survival of 18 months.

MEMORIAL SLOAN-KETTERING CANCER CENTER IRB PROTOCOL

IRB#: 11-107A(12)

Patients relapsing with an insidious or classical form of disease with skeletal events only, or after a long lasting first response were likely to respond well to conventional salvage therapy. In contrast, relapse with multiple symptoms, transformed disease or a short duration of first response implied bad prognosis. Of the 162 patients who relapsed 49% received a melphalan based salvage regimen with 59% having at least a 25% reduction in tumor burden, 34% received a VAD like re-induction with a 46% response rate, 8% received thalidomide with a 67% response rate and 8% received a second autograft as salvage therapy with an 83% response rate. Response to relapse therapy was important for survival after relapse. Patients with a partial response or better to relapse therapy had a median survival of 36 months vs 37 months for minor responders and 8 months for nonresponders. The median survival after start of relapse therapy was 33 months for complete and partial responders and 26 months for minor responders and 7 months for non responding patients. Sixty-one patients have been treated for subsequent.

More recently Kumar et al reported on the outcomes of patients relapsing after autologous transplant in the era of lenalidomide and bortezomib therapy³⁶. Among 494 patients, undergoing auto-SCT within 12 months of diagnosis they identified 124 patients who had relapsed within 12 months of high dose therapy, this group had a significantly shorter median overall survival (OS) from diagnosis (26.6 vs 90.7 months) and from SCT than those relapsing later in the course of their disease. Median survival from relapse was only 10.8 months in the early relapse group compared to 41.8 months for the rest. Among the 97 patients who relapsed early after transplant, patients who received thalidomide, bortezomib and/or lenalidomide) had a better survival than those that did not receive those drugs 15.9 months vs 4.5 months. Benefits of exposure to lenalidomide, bortezomib or thalidomide were confirmed in a larger series of 387 patients reported by the same authors. Those relapsing after the year 2000 had a median overall survival of 23.9 versus 11.8 months ($P < .001$) for those who relapsed prior to this date. Patients treated with thalidomide, lenalidomide, or bortezomib had longer survival from relapse (30.9 vs 14.8 months; $P < .001$)³⁷.

With the results of CALGB100104 and IFM05 it is likely that many patients will now be relapsing on lenalidomide maintenance which consists of lower doses of lenalidomide without dexamethasone. Based on the results of the phase I study of lenalidomide we hypothesize that intensifying the dose of lenalidomide could potentially re-establish control of the disease in up to 30% of myeloma patients with asymptomatic relapses, therefore saving the use of other agents for future use.

3.2.2.2 MSKCC Experience with Relapse after HDM/ASCT

We have recently reviewed the pattern of relapse in 40 patients who have participated in CALGB 100104 clinical trial and enrolled at MSKCC between 2005 and 2009. Among these 40 patients, relapse from CR or progression has occurred in 16 patients. The first evidence for relapse/progression was detected by Immunofixation in four patients who were in CR; SPEP with increase in M spike in five patients (3 who were in PR and 2 in VGPR); and free light chain assay in five patients (four who were in CR and one in PR). Only two among the 16 patients were found to have relapse/progression of disease after development of symptoms due to organ damage, triggering an evaluation by MRI that lead to the diagnosis of relapse/progression. This data would

MEMORIAL SLOAN-KETTERING CANCER CENTER IRB PROTOCOL

IRB#: 11-107A(12)

indicate, contrary to the previous two reports detailed above by Lenhoff et al. and Alegre et al., that asymptomatic relapse (referred to as insidious relapse by these authors) is currently the most common pattern of relapse nowadays. This is most likely related to the availability of the free light chain assay which allows earlier detection of disease relapse and progression. In addition, the prospective aspect of the CALGB 100104 clinical trial that called for a rigorous monitoring of the patients every three months, certainly contributed to the earlier detection of relapse and progression prior to the development of organ damage. Despite the small sample of this observation, we are confident that the most common form of relapse and/or progression in patients receiving maintenance therapy after HDM/ASCT is asymptomatic. Hence, we anticipate that patient recruitment within this population will be facilitated.

4.0 OVERVIEW OF STUDY DESIGN/INTERVENTION

4.1 Design

In this multi-center Phase II single arm trial, 53 patients fulfilling the eligibility criteria, will be treated with lenalidomide 25 mg PO daily for 21 out of 28 day cycles. The patients' responses to the treatment will be assessed after every cycle. Patients who have asymptomatic POD after 2 cycles will have dexamethasone added at a dose of 40 mg PO weekly. Patients who have at least SD after 2 cycles will continue lenalidomide single agent until asymptomatic POD, at which time they will have dexamethasone added at a dose of 40 mg PO weekly. Patients will be taken off study if they have symptomatic POD after any cycle, if they have any type of POD after dexamethasone is added, or if they do not tolerate the treatment. The patients taken off study due to any type of POD, will be considered failures for the primary response endpoint if progression occurred within 6 months. Patients who are removed from study prior to completing 2 cycles of therapy for reasons other than POD will be considered inevaluable for response and will be replaced. Accrual will continue until 53 evaluable patients have been accrued. Patients who have received any study drug will be evaluated for safety.

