9.0 TREATMENT/INTERVENTION PLAN

9.1 Treatment Plan

- Lenalidomide dose will begin at 25 mg PO daily for 21 days of a 28-day-cycle adjusted for toxicity, if necessary. Once the dose of lenalidomide is reduced for toxicity, no dose-re- escalation is permitted.
- If a dose of lenalidomide is missed, it should be taken as soon as possible on the same day. If it is missed for the entire day, it should not be made up.
- Patients taking more than the prescribed dose of lenalidomide should be instructed to seek emergency medical care if needed and contact study staff immediately.
- Only one cycle of therapy may be dispensed to the patient each month. Lenalidomide capsules should be swallowed whole, and should not be broken, chewed or opened.
- Special Handling Instructions: Females of childbearing potential should not handle or administer lenalidomide unless they are wearing gloves.
- Record of administration: Accurate records will be kept in the source documents of all drug administration (including prescribing and dosing). Patients will be instructed to bring their complete medication diary (refer to Appendix D) to each study visit for assessment of compliance.

MEMORIAL SLOAN-KETTERING CANCER CENTER IRB PROTOCOL

IRB#: 11-107A(12)

- Patient will be evaluated for response and toxicity after every cycle and the response to lenalidomide intensification will be assessed after every cycle of therapy.
 - Patients with at least SD after 2 cycles of lenalidomide will continue on lenalidomide until asymptomatic POD at which time dexamethasone will be added at a dose of 40 mg PO weekly for the next cycle.
 - Patients with asymptomatic POD after 2 cycles of lenalidomide will have dexamethasone added to lenalidomide at a dose of 40 mg PO weekly with the next cycle.
 - Patients with further asymptomatic POD after any cycle of lenalidomide and dexamethasone will be taken off study and treated at the discretion of the treating physician. Note that further POD after the addition of dexamethasone will be determined compared to the new M spike baseline just prior to the addition of dexamethasone.
- Once patients are started on dexamethasone, they will also receive prophylaxis medication including Bactrim DS, one tablet PO TIW, fluconazole, 100 mg PO Daily, ASA 81 mg PO daily, and a PPI.
- Note that patients with symptomatic POD at any point in time during treatment will be taken off study.

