13.0 CRITERIA FOR REMOVAL FROM STUDY

Treatment with study drugs is to be discontinued when any of the following occurs:

- Symptomatic POD, i.e. *with organ damage* at any point in time during the treatment
- Asymptomatic POD, i.e. *without organ damage* after at least one cycle of lenalidomide and dexamethasone
- Adverse event(s) that, in the judgment of an Investigator, may cause severe or permanent harm or which rule out continuation of study drug

MEMORIAL SLOAN-KETTERING CANCER CENTER IRB PROTOCOL

IRB#: 11-107A(12)

- Major violation of the study protocol
- Withdrawal of consent
- Patient is lost to follow-up
- Suspected or confirmed pregnancy. If pregnancy or a positive pregnancy test does occur in a study subject or the partner of a male study subject during study participation, study drug must be immediately discontinued.

Any possible premature discontinuation would be documented adequately with reasons being stated, and information would have to be issued according to local requirements (e.g., IRB, regulatory authorities, etc.).

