14.0 BIOSTATISTICS

The primary objective of this study is to estimate overall response rate (\geq PR) to lenalidomide intensification with or without dexamethasone at 6 months. A single stage design that differentiates between response rates of 15% and 30% will be used to assess efficacy of lenalidomide intensification with or without dexamethasone.

The probabilities of a type I error (falsely accepting a non-promising therapy) and type II error (falsely rejecting a promising therapy) are set to 0.10 and 0.10, respectively. The null hypothesis response rate is based on the response rates ranging from 12.5% to 16.4% to the standard of care therapy in patients previously exposed to thalidomide who have relapsed or refractory disease (reference Webber and Dimopoulos papers^{38,39}). A total of 53 patients will be accrued. At the conclusion of the study, if a least 12 of the 53 patients respond by 6 months the treatment will be declared a success. At the end of the study, the response rate will be estimated and a confidence interval will be constructed.

We expect to accrue 53 patients in two years with approximately 10-15 patients accrued from MSKCC and the remaining patients accrued from the other centers.

The incidence of toxicities of grade 2 or higher toxicities (CTCAE version 4.0), the incidence of probable viral fungal and bacterial infections, and the incidence of treatment-related mortality, i.e., from causes other than relapse or progression, will be recorded for each patient after each cycle and at the end of study visit. Safety data will be described in a variety of ways, both graphically and in tabular form.

Progression free survival is defined as the time from treatment initiation to relapse/progression, death, initiation of non-protocol anti myeloma therapy, or last follow-up. Overall survival is defined as time from treatment initiation until death or last follow-up. Progression free and overall survival will be estimated using the Kaplan-Meier method.

We will estimate the response rate (CR, VGPR, and PR) by 6 months from initiation of lenalidomide intensification of lenalidomide given as single agent. For this calculation, patients who have asymptomatic progression after 2 cycles of lenalidomide and receive dexamethasone will be considered failures.

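### Section 4.1 chooses between failure and replacement by the recorded reason for leaving, so a patient with documented progression after cycle 1 who leaves early for another reason is replaced, not counted as a non-responder

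*Combined protocol and SAP*

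**What the plan says.** **Scoring (Section 4.1).** Patients taken off study because of POD of any type are failures for the primary endpoint if the progression fell within 6 months. For early leavers, "Patients who are removed from study prior to completing 2 cycles of therapy for reasons other than POD will be considered inevaluable for response"; they are replaced, and accrual runs until 53 evaluable patients are in. Both rules look at why the patient left.

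**Removal.** Section 4.1 states: "Patients will be taken off study if they have symptomatic POD after any cycle, if they have any type of POD after dexamethasone is added"; its only other ground is intolerance. Section 13.0 lists symptomatic POD at any time, but asymptomatic POD only "after at least one cycle of lenalidomide and dexamethasone". Its other grounds include adverse events, major protocol violation, withdrawal of consent and loss to follow-up.

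**Assessment.** Section 9.1 says: "Patient will be evaluated for response and toxicity after every cycle". Sections 1.4, 4.1 and 9.1 attach the addition of dexamethasone to asymptomatic POD after 2 cycles, and Section 4.2 to POD after 2 or more. None says how asymptomatic POD found after cycle 1 is handled or scored.

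**Test (Section 14.0).** "A single stage design that differentiates between response rates of 15% and 30% will be used"; the type I and type II error probabilities "are set to 0.10 and 0.10, respectively"; "A total of 53 patients will be accrued"; and "if a least 12 of the 53 patients respond by 6 months the treatment will be declared a success". Section 14.0 contains no rule that overrides the replacement rule. Its one extra failure rule concerns the secondary single-agent endpoint.

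**The concern.** Replacing early leavers is usually defended on the ground that their outcome is unknown. Here part of it is known: the disease was seen to progress within the 6-month window, which is the event that Section 4.1 counts as failure when it is the recorded reason for leaving. Two patients with the same disease course can be scored differently because of one field on the off-study form, and different centers may fill in that field differently.

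The error runs one way. A patient who leaves without a response is taken out of the denominator, and the replacement may respond. The observed rate can only be pushed up, and with it the chance of declaring success.

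**Working it through.** **1. Which patients are affected.** Take a patient with asymptomatic POD documented after cycle 1, still on lenalidomide alone, who leaves before completing cycle 2.

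| Recorded reason for leaving | Score under Section 4.1 |
|---|---|
| POD (any type) | Failure, stays in the 53 |
| Adverse event, withdrawal of consent, loss to follow-up | Inevaluable, replaced |

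Symptomatic POD is not affected: it is a removal reason at any time and is scored a failure. A patient who stays on study is not affected either.

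**2. The plan's own figures.** Inputs from Section 14.0: n = 53, success if at least 12 respond, null rate 0.15, alternative rate 0.30. Exact binomial:

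- P(X ≥ 12 | 53, 0.15) = 0.0907, within the 0.10 limit.
- P(X ≥ 12 | 53, 0.30) = 0.909, which meets the 0.90 target.

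The design reproduces, and 53 with a cut-off of 12 is the smallest exact design that meets both limits. The room under 0.10 is 0.10 − 0.0907 = 0.0093.

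**3. Effect of replacement.** Let k such patients be replaced, so that 53 + k are treated and the replaced share is f = k/(53 + k). Let s be the chance that a replaced patient would have responded by 6 months had he or she stayed. With a true rate of 0.15 in all treated patients, the rate among evaluable patients is

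p = (0.15 − f·s)/(1 − f).

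For k = 1 and s = 0: f = 1/54 = 0.0185, so p = 0.15 × 54/53 = 0.1528. For k = 2 and s = 0: f = 2/55 = 0.0364, so p = 0.15 × 55/53 = 0.1557.

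P(X ≥ 12 | 53, p):

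| k | s = 0 | s = 5% | s = 10% |
|---|---|---|---|
| 0 | 0.091 | 0.091 | 0.091 |
| 1 | 0.101 | 0.098 | 0.094 |
| 2 | 0.112 | 0.105 | 0.098 |

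Both k and s are assumptions; the documents give neither.

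**4. Effect on the estimate.** At the cut-off, 12/53 = 22.6%. With one dropped patient counted it is 12/54 = 22.2%; with two, 12/55 = 21.8%.

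**The case against.** Four arguments on the other side have weight.

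- **A site can record POD.** A reader might infer that every cycle 1 progressor who leaves early must be replaced. The documents do not support that. The failure rule covers POD of any type, and nothing in Section 13.0 forbids recording POD as the reason. If the patient stops because of the progression, failure is the natural score. What stands is the narrower case of a different recorded reason, with no rule on which reason prevails.
- **Cycle 1 POD is not itself a primary failure.** A reader might infer that a known treatment failure is being thrown away. But the primary endpoint allows response with or without dexamethasone, and asymptomatic POD after 2 cycles leads to dexamethasone. A patient who stays can still respond. One who leaves has observed progression and no response so far, but an unobserved 6-month outcome. That is why s appears in the formula.
- **The size has no source.** Section 3.2.1 reports 16% progressive disease in an earlier randomized phase II study, and a reader might take this as the early progression rate here. It cannot serve. No time point is given, asymptomatic POD is not separated, the doses and the heavily pre-treated population differ, and the cited title covers lenalidomide alone or with dexamethasone.
- **Few patients are likely.** Early asymptomatic POD and departure for an unrelated reason must fall within about one 28-day cycle. If the replaced share of treated patients is 1.6% or less, the error stays under 0.10 even with s = 0 (0.0996 at 1.6%).

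These arguments limit the size. They do not remove the gap in the rule or change the direction of the bias.

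**Conclusion.** The concern holds as a minor point. As written, a patient with POD documented after cycle 1 who leaves before completing 2 cycles for a reason other than POD is dropped and replaced, although progression was observed and no response was reached. The bias favors declaring success. With 0 to 2 such patients (assumed), the exact type I error lies between 0.091 and 0.112 if none of them would have responded, and lower if some would. The sample size and cut-off are correct as stated; the fault lies only in who enters the denominator.

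**What to change.** In Section 4.1, mirrored in Section 14.0, state for the primary endpoint:

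- A patient removed within 6 months, with POD by the Section 12.0 criteria documented at or before removal and no PR or better by then, counts as a non-responder whatever reason for removal is recorded.
- Only patients removed before completing 2 cycles with no documented POD are inevaluable and replaced.

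This uses assessments that are already collected and leaves n = 53 and the cut-off of 12 unchanged. The cost is a slightly lower observed response rate if such patients occur; slightly fewer replacements would be needed.

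Separately, the handling of asymptomatic POD after cycle 1 is not stated in Sections 1.4, 4.1, 4.2, 9.1 or 13.0. The sponsor should reconcile those sections. That is a clinical decision, and none is proposed here.
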